1.6.1 Rationale for combination of pembrolizumab with chemotherapy for cohorts A and B

The combination of PD-1 inhibition with chemotherapy is attractive for several reasons. First, if chemotherapy creates tumor lysis that can lead to the uptake and presentation of tumor antigens that can promote immune responses, the combination of then blocking the PD-1 checkpoint may offer synergy in boosting the immune response. This idea will be explored in cohort B, where participants will have received 1 cycle of chemotherapy prior to entering study. Second, if PD-1 inhibition can augment the immune response initially, this may allow for synergistic killing of cancer cells from two sides (CD8 cells and direct cytotoxic activity of chemotherapy) upfront. This idea will be explored in cohort A, where pembrolizumab and chemotherapy are combined upfront. Finally, if initial exposure to chemotherapy or radiation can upregulate PD-L1 expression, this may signal a timeframe during which PD-1 inhibition can be most effective (an idea which will be explored in this study in cohorts B-D).

The safety and efficacy of pembrolizumab with platinum-based regimens is actively being explored including in KEYNOTE-021, which is a study in non-small cell lung cancer combining pembrolizumab with carboplatin + paclitaxel (+/- bevacizumab) and carboplatin + pemetrexed. Other studies have combined other anti PD-1/PD-L1 antibodies with similar platinum doublets. To date, there have not been clearly adverse safety signals seen and no clear reason to think that a combination with platinum + etoposide would be different given known toxicity profiles of these agents or pembrolizumab. In order to establish safety, however, an initial cohort of 3 participants will be enrolled and once safety has been determined, an additional 3 participants will be enrolled. If safety is adequate in these 6 participants, enrollment will continue, but if not, combination therapy will be re-evaluated (see section 5.3.1 for details).

1.7 Correlative Studies Background

Immunohistochemistry:

PD-L1 has been studied extensively in studies of pembrolizumab and other PD-1/PD-L1 inhibitors with mixed results, although this has been attributed to variability in different assays and in different definitions of positivity. In NSCLC, pembrolizumab activity was significantly better in patients who had high levels of TUMOR cell expression of PD-L1²⁰ although the data are more mixed for nivolumab²⁷. Atelolizumab had higher activity either in the setting of high tumor cell expression or immune infiltrate expression with improved outcomes in those settings.

There is less data on whether PD-L1 positivity is common in other thoracic malignancies such as small cell lung cancer (SCLC) and it is thought that the rate of positivity may be much lower in SCLC, although this determination is based solely on archival tissue evaluation primarily from surgical resections²⁶. There is some data that immune infiltrate may be more prevalent in SCLC and the relative importance of PD-L1 expression in each of these compartments remains to be determined for SCLC.

SCLC is also unique compared to both NSCLC and melanoma in that it demonstrates robust response rates to both chemotherapy and radiation, both of which could modulate PD-L1 expression. Therefore, PD-L1 expression and the degree of immune infiltrate could change in response to therapy and influence the effectiveness of anti-PD-1 therapy.

This study will evaluate cohorts of patients receiving pembrolizumab prior to any therapy (cohort A), after 1-2 cycles of chemotherapy (cohort B), after completion of 1st line chemotherapy (cohort C), and after completion of radiotherapy (cohort D) to evaluate changes in PD-L1 expression as assessed by immunohistochemistry compared to pre-treatment samples. In addition, CD3 immunostaining will be performed to evaluate the degree of immune infiltrate in tumor specimens pre- and post-chemotherapy or radiotherapy. Finally, other markers of immune suppression will be simultaneously evaluated in all specimens. [name] of NYU has developed a quantitative immunofluorescence platform that

can simultaneously measure up to 7 markers. This assay is currently being optimized on lung cancer specimens and will be used as the methodology of evaluation in this study. The current optimized markers are PD-1, PD-L1, CD3, CD8, CD163, and IDO1.

DNA sequencing

Neoantigen load has been proposed as an important biomarker of potential sensitivity to PD-1 and PD-L1 inhibition in multiple tumor types²⁸, and compared to other malignancies, small cell lung cancer has a high mutational burden due to the very high association with heavy smoking. Given the reported lower level of PD-L1 expression in SCLC, mutational burden may be a relatively more important biomarker in this setting.

We will plan to conduct whole-exome sequencing on a subset of patients in collaboration with the Broad Institute.

Gene Expression

Inflammatory or immune-related gene expression signatures have been suggested to serve as predictors of clinical benefit beyond PD-L1 expression in multiple tumor types treated with pembrolizumab^{29,30} and will be evaluated using nanostring in pre-treatment biopsies on this study.

Immune profiling in tumor biopsies is actively under evaluation at the Belfer Center for Applied Cancer Science at DFCI and in [name]'s lab at NYU to understand correlates of response and resistance. Preliminary data has been generated in both mesothelioma and NSCLC and we are currently generating data from SCLC samples as well using fresh tissue that is dissociated and subject to flow cytometry using antibodies specific for the following human markers: CD3 (HIT3a; UCHT1), CD8 (RPA-T8), CD14 (M5E2; MphiP9), CD24 (ML5), CD45 (HI30), CD56 (B159), CCR7 (150503), EpCAM (EBA-1), HLA-DR (G46-6), PD-1 (EH12.1), and IgG1 isotype control (MOPC-21) from BD Biosciences (San Jose, CA); CD3 (UCHT1), CD4 (RPA-T4), CD14 (M5E2), CD15 (W6D3), CD16 (3G8), CD19 (HIB19), CD20 (2H7), CD21 (Bu32), CD25 (BC96), CD27 (M-T271), CD33 (WM53), CD38 (HIT2), CD40L (24-31), CD45 (HI30), CD45RA (HI100), CD45RO (UCHL1), CD56 (HCD56; 5.1H11), CD66b (G10F5), CD69 (FN50), CD83 (HB15e), CD123 (6H6), CD160 (BY55), CD163 (GHI/61), CTLA-4 (L3D10), CXCR5 (J252D4), EpCAM (9C4), HMGB1 (3E8), IgM (MHM-88), Ki-67 (Ki-67), PD-1 (EH12.2H7), PD-L1 (29E.2A3), PD-L2 (24F.10C12), TIM-3 (F38-2E2), NKG2D (1D11), NKp46 (9E2), IgG2a isotype control (MOPC-173), IgG2b isotype control (MPC-11), and IgG1 isotype control (MOPC-21) from BioLegend (San Diego, CA); Pan-cytokeritin (C11) and PD-L1 (E1L3N) from Cell Signaling Technologies (Danvers, MA); CD45 (2D1), FOXP3 (236A/E7), and IL-10 (236A/E7) from Affymetrix/eBioscience (San Diego, CA); LAG3 (polyclonal) and isotype control (polyclonal) from R&D Systems (Minneapolis, MN).

Soluble PD-L1 analysis from peripheral blood samples has been extensively studied in melanoma in [name]'s lab, Dana Farber Cancer Institute and is now being evaluated in all tumor types under the Center for Immuno-Oncology core facility.

Circulating tumor DNA

[name] and colleagues in concert with the Broad Institute initiatives under [name] have demonstrated that accurate and powered WES of circulating tumor cells (CTCs) is both possible and likely useful clinically⁷⁴. This was first established in experimental and analytical workflows for census-based sequencing of single CTCs and then validated in patients with metastatic prostate cancer. The approach is currently being validated in other tumor types including SCLC. This same approach is also being extended to the sequencing of tumor-derived cfDNA and we have preliminary data demonstrating consistent adequate purity and yield of tumor-derived DNA for WES from SCLC samples.

Blood sample collections will occur at baseline for all participants, prior to the start of immunotherapy for cohorts A and B, and at the time of progression for all participants. Each blood sample would be processed for cfDNA, and germline DNA. The extraction of cfDNA and germline DNA will be performed from frozen aliquots of plasma and white blood cells, respectively. The yields and purities of cfDNA will be assessed prior to WES with ultra-low-pass (ULP) sequencing. It has been recently demonstrated

that the yield and purity of cfDNA from a set of previously collected SCLC plasma samples is adequate for sequencing (25-30%) with variance in the quantity through the course of therapy. In addition to evaluating genomic alterations and neoantigen profile changes as a result of exposure to therapy in DNA extracted from blood, the findings will be compared to parallel sequencing analysis done on tissue biopsies from the same subjects to compare similarities and any potential differences. This analysis will help us to determine whether cfDNA sequencing may be a possible substitute for tissue-based sequencing which would be critical particularly in this tumor type given the difficulty in obtaining adequate tissue for molecular analysis. We will also evaluate quantitative changes in tumor-derived cfDNA through the course of therapy to determine correlation with tumor burden.

1.8 Research Risks & Benefits

1. Risk of Study Drug

Pembrolizumab

Very common, side effects seen in (> 20% chance this will happen):

- Itching of the skin
- Loose or watery stools
- Cough

Common, side effects seen in (≥ 10% to 20% chance this will happen):

- Joint pain
- Rash
- Fever
- Back pain
- Pain in your belly
- Loss of skin color
- Not enough thyroid hormone so you may feel tired, gain weight, feel cold, have infrequent or hard stools
- Low levels of salt in the blood that may cause you to feel tired, confused, have a headache, muscle cramps and/or feel sick to your stomach

Uncommon, side effects seen (>1% to < 5% chance this will happen)

- Inflammation of the lungs so you may feel short of breath and cough.
- Too much thyroid hormone so you may feel anxious, angry, have trouble sleeping, feel weak, tremble, sweat, feel tired, have loose and watery stools
- Infusion reaction, where you may feel dizzy or faint, flushed, get a rash, have a fever, feel short of breath at the time of receiving your infusion (IV) or just after, or pain at the site of infusion
- Inflammation of the bowels/gut, which may cause severe pain in your belly with loose or watery stools, and black, tarry, sticky stools or stools with blood or mucus
- Inflammation of the skin so you may have peeling of the skin, itchiness, and/or skin redness. The skin inflammation (i.e. peeling, itching and redness) could also be widespread throughout your body. More severe skin reactions may involve the inside of your mouth, the surface of your eye and genital areas, and/or may cause the top layer of your skin to peel from all over your body which can cause severe infection.

Rare, side effects seen in (<1% chance this will happen)

- Inflammation of the nerves that may cause pain, weakness or tingling in your hands and feet, and may spread to your legs, arms and upper body leading to severe muscle weakness and possible temporary paralysis
- Inflammation of the muscles so you may feel weak or have pain in your muscles
- Inflammation of the pancreas (a gland in your abdomen that controls sugar levels) so you may have severe pain in the top part of your belly that may move to your back, feel sick to your stomach, and vomiting that gets worse when you eat
- Inflammation of the eye so you may have eye redness, blurred vision, sensitivity to light, eye pain, see floaters or have headaches
- Inflammation of the liver that may make you feel sick to your stomach and vomit, feel like not eating, feel tired, have a mild fever, have a pain in the right side of your belly, yellow eyes and skin, and dark urine
- Inflammation of the pituitary gland (a gland in the head), which may cause you to feel sick to your stomach or have headaches, changes in your behavior, double vision, few to no menstrual cycles, weakness, vomiting and dizziness or fainting
- Adrenal glands (glands on top of the kidneys) that may not make enough hormone, which could cause tiredness, weight loss, muscle weakness, feeling faint, joint, muscle and belly aches, nausea, vomiting, loose or watery stools, fever, salt craving, and sometimes darkening of the skin like a suntan
- Type 1 Diabetes, a condition that can cause too much sugar in your blood, feeling thirstier than usual, frequent urination and weight loss. You are likely to need regular insulin shots.
- Inflammation of the kidney so you may pass less urine or have cloudy or bloody urine, swelling and low back pain
- Inflammation of the middle layer of your heart wall that may cause your heart to have difficulty pumping blood throughout your body, which can cause chest pain, shortness of breath and swelling of the legs. You may experience a fast or irregular heartbeat that may cause dizziness or fainting.
- Inflammation of the thyroid gland, an organ that makes and stores thyroid hormones. This condition may lead to change in your heart rate, blood pressure, body temperature, and the rate at which food is converted into energy.
- A condition that may make you feel weak and tired and might have drooping of the eyelids, blurred or double vision, difficulty swallowing, slurred speech, weakness in your arms and legs, or difficulty breathing
- The formation of small clusters of immune cells (called granulomas) in parts of your body such as your lymph nodes, eyes, skin, or lungs
- Inflammation of the brain with confusion and fever. This may also include: disorientation, memory problems, seizures (fits), changes in personality and behavior, difficulty speaking, weakness or loss of movement in some parts of your body, and loss of consciousness

Additionally, since pembrolizumab was approved in September 2014, the following side effects have been reported by people receiving pembrolizumab. These side effects were voluntarily reported from a group of people of unknown size. It is not possible to estimate the frequency of this side effect:

- Inflammation of the joints which may include joint pain, stiffness and/or swelling

If you have had an allogeneic stem cell transplant (a procedure in which a person receives blood-forming stem cells from a donor), you may experience graft versus host disease (GvHD), which may include diarrhea, skin rashes, and liver damage, after receiving pembrolizumab. Sometimes this condition can lead to death.

If you have had a solid organ transplant (for example, if you have received a kidney or heart transplant), you may experience rejection of the transplanted organ. Your doctor will monitor you and should tell you what signs and symptoms you should report depending on the type of transplant you have had.

-
-

-
-

2. Other Risks of Study Participation

Additional risks to study participation include breach of confidentiality and risks associated with blood draw. Privacy procedures in place and good clinical practice guidelines are followed for the study to minimize risks associated with research procedures and participation. The risks associated with blood draw include weaknesses, redness, pain, bruising, bleeding or infection at the needle site.

3. Potential benefits

The potential benefits to subjects with study participation are improved overall survival. The information obtained from this research may help others with this disease in the future.

2 Study Objectives

2.1 Primary Objectives

Primary Objective:

- To determine PD-L1 expression status in subjects with SCLC and assess changes in expression following chemotherapy and radiation in pre-specified cohorts of SCLC.
 - A—subjects who are chemotherapy and radiation naïve
 - B—subjects who have had 1 prior cycle of 1st line chemotherapy with cisplatin or carboplatin + etoposide for extensive-stage SCLC
 - C—subjects who have completed 4-6 cycles of chemotherapy with cisplatin/carboplatin + etoposide and are not going to receive further radiation therapy
 - D—subjects who have completed 4-6 cycles of cisplatin/carboplatin + etoposide and consolidation thoracic radiation therapy (with or without the addition of prophylactic cranial irradiation)

2.2 Secondary Objectives

- To evaluate median and progression-free survival at 3 and 6 months with the addition of pembrolizumab to standard therapy
- To evaluate median overall survival and overall survival at 6 months with the addition of pembrolizumab to standard therapy
- To evaluate response rates at 6 and 12 weeks by RECIST 1.1 and irRECIST with the addition of pembrolizumab to standard therapy
- To evaluate safety profile of pembrolizumab in combination with standard therapy for small cell lung cancer.

2.3 Exploratory Objectives

- To evaluate soluble PD-L1, circulating cytokines, and circulating T cell repertoire before, during, and after therapy with pembrolizumab and their relationship to clinical benefit with

pembrolizumab therapy.

- To evaluate genetic changes using nextgen sequencing (oncopanel) and gene expression changes using nanostring before, during, and after therapy with pembrolizumab and determine relationship, if any, to clinical benefit with pembrolizumab. If feasible, will also perform whole-exome sequencing on a subset of tumor biopsies to evaluate mutational burden prior to treatment with pembrolizumab and determine relationship to clinical benefit.

3 Study Design

3.1 General Design

This is a phase II study of pembrolizumab therapy initiated at different times during the course of SCLC treatment: **a)** up front, in conjunction with initiation of chemotherapy, **b)** starting after one cycle of chemotherapy, **c)** starting after completion of 1st line chemotherapy, and **d)** starting after completion of consolidation thoracic radiation therapy.

Treatment with pembrolizumab will be preceded by biopsy for evaluation of PD-L1 expression at baseline prior to any treatment (cohort A); after short-term exposure to chemotherapy (cohort B); after completion of chemotherapy (cohort C, which will include both patients with chemotherapy-sensitive disease (stable/continued response) and those with chemotherapy-refractory disease (progression within 60 days of completion of treatment with carboplatin-etoposide); and after exposure to radiation therapy (cohort D). These timed biopsies will permit correlative evaluation of changes in PD-L1 expression (relative to diagnostic biopsy) and changes in other tissue and blood based immune markers before, during, and after therapy.

3.2 Primary Study Endpoints

- To determine PD-L1 expression status in subjects with SCLC and assess changes in expression with chemotherapy and radiation
–We will evaluate PD-L1 expression as determined by immunohistochemistry in pre-treatment and archival samples.

3.3 Secondary Study Endpoints

- To evaluate progression-free survival with the addition of pembrolizumab to standard therapy
 - endpoint: to evaluate median progression-free survival in overall population with stratification by cohort as compared to historical control of 5.4 months³¹
- To evaluate overall survival with the addition of pembrolizumab to standard therapy
 - Endpoint: to evaluate median overall survival in overall population with stratification by cohort as compared to historical control of 9.5 months.³¹
- To evaluate response rates by RECIST 1.1 and irRC (as adapted to RECIST 1.1³²) with the addition of pembrolizumab to standard therapy (for cohort A only)
 - Endpoint: response rate at 6 and 12 weeks after initiation of pembrolizumab therapy as measured by RECIST 1.1 and irRC (as adapted to RECIST 1.1³²)

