3. TREATMENT PLAN

Each cohort will consist of 15 patients. All patients will be treated with up to 6 cycles of cis/carboplatin + etoposide. Eligible patients for consolidation thoracic radiotherapy will complete this within 6 weeks following completion of chemotherapy. All patients will be required to have pre-treatment biopsies prior to initiation of pembrolizumab for evaluation of PD-L1 expression and other correlative evaluations (within 4 weeks of start). Cohorts B-D will ALSO be required to submit a diagnostic biopsy specimen (prior to any treatment) for intra-subject comparison of PD-L1 expression between biopsies.

Cohort A will start pembrolizumab at the same time as starting standard chemotherapy with carboplatin + etoposide and receive all three drugs. Cohort B will start pembrolizumab after one cycle of cis/carboplatin/etoposide and receive all three drugs for the remaining cycles. Cohort C will consist of subjects who are not candidates for consolidation thoracic radiotherapy (thoracic RT) or prophylactic cranial irradiation (PCI) but who have completed 1st line therapy with 4-6 cycles of chemotherapy—these subjects will start pembrolizumab after completion of chemotherapy. Cohort D will consist of patients who have completed 4-6 cycles of carboplatin + etoposide as well as consolidation thoracic radiotherapy and/or PCI—these subjects will start pembrolizumab after completion of chemotherapy and radiation.

Pembrolizumab will be continued until progression following completion of standard treatment for all cohorts or for up to 2 years of therapy total.

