4.1 Eligibility/Inclusion Criteria

1. Participants must have histologically confirmed small cell lung carcinoma not amenable to initial concurrent radiotherapy (extensive-stage disease).
2. Participants may have evaluable or measurable disease, defined as at least one lesion that can be accurately measured in at least one dimension (longest diameter to be recorded for non-nodal lesions and short axis for nodal lesions) as ≥ 20 mm with conventional techniques or as ≥ 10 mm with spiral CT scan, MRI, or calipers by clinical exam. See Section 7.0 for the evaluation of measurable disease.
3. Participants in cohort B must have completed 1 cycle of systemic chemotherapy. Therapy with the combination must start no sooner than 3 weeks from the last dose of chemotherapy and no later than 5 weeks from the last dose of chemotherapy. Participants in cohort B must not have had progression of disease prior to the start of therapy.
4. Participants in cohort C must have completed systemic therapy (4-6 cycles cisplatin or carboplatin + etoposides) and NOT be a candidate for consolidation thoracic radiotherapy or PCI. Participants in cohort C must initiate therapy with pembrolizumab within 6 weeks of the last dose of chemotherapy (therapy must not start within 2 weeks from the last dose). Participants in cohort C must not have had progression of disease prior to the start of therapy.
5. Participants in cohort D must have completed systemic therapy AND have completed either consolidation thoracic radiotherapy or PCI or both completed either consolidation thoracic radiotherapy or PCI or both. Participants in cohort D must initiate therapy with pembrolizumab within 6 weeks of the last dose of radiation. Therapy must not start within 2 weeks from the

last dose. **Consolidation radiotherapy dose must NOT be more than 3000 cGy.**
 Participants in cohort D must not have had progression of disease prior to the start of therapy.

6. Age > 18 years.
7. ECOG performance status ≤ 2 (Karnofsky $\geq 60\%$, see Appendix A)
8. Life expectancy of greater than 3 months.
9. Participants must have normal organ and marrow function during screening and on Cycle 1, day 1 as defined below:

Table 1 Adequate Organ Function Laboratory Values

System	Laboratory Value
Hematological	
Absolute neutrophil count (ANC)	$\geq 1,500$ /mcL
Platelets	$\geq 100,000$ / mcL
Hemoglobin	≥ 9 g/dL or ≥ 5.6 mmol/L without transfusion or EPO dependency (within 7 days of assessment)
Renal	

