4.2 Exclusion Criteria

1. Participants in cohort A may not have had prior therapy for their disease. Participants in cohort B may not have had more than 1 cycle of systemic therapy (cisplatin or carboplatin + etoposide). Participants in cohort C and D should not have had more than one prior regimen of chemotherapy.
2. For participants entering cohorts C or D, prior treatment-related toxicities should have resolved to grade 1 or baseline (with the exception of anemia (as per inclusion criteria, alopecia, and neuropathy (≤ grade 2 allowed)).
3. Participants who have had a CR after pre-study therapy are not eligible for study.
4. No thoracic radiation > 3000 cGy allowed.
5. Prior radiation or surgery must have completed at least 2 weeks prior to initiation of therapy and all toxicities or complications from these must have resolved to baseline or grade 1 prior

to starting therapy (with the exception of anemia (as per inclusion criteria, alopecia, and neuropathy (\leq grade 2 allowed)).

6. No stroke, myocardial infarction, or major surgery within 3 months of starting on therapy.
7. Participants who are receiving any other investigational agents or have received investigational therapy or any anti-cancer monoclonal antibody (mAB) within 4 weeks prior to the 1st dose of pembrolizumab.
8. Has received prior therapy with an anti-PD-1, anti-PD-L1, or anti-PD-L2 agent.
9. Has active autoimmune disease that has required systemic treatment in the past 2 years (i.e. with use of disease modifying agents, corticosteroids or immunosuppressive drugs). Replacement therapy (eg., thyroxine, insulin, or physiologic corticosteroid replacement therapy for adrenal or pituitary insufficiency, etc.) is not considered a form of systemic treatment.
10. Has known history of non-infectious pneumonitis which required steroids, or any evidence of current, non-infectious pneumonitis.
11. Has an active infection requiring systemic therapy.
12. Has a diagnosis of immunodeficiency or is receiving systemic steroid therapy or any other form of immunosuppressive therapy within 7 days prior to the first dose of trial treatment.
13. Has a known history of active TB (Bacillus Tuberculosis)
14. History of allergic reactions attributed to compounds of similar chemical or biologic composition to pembrolizumab, cisplatin, carboplatin, or etoposide.

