FOR COHORTS A AND B ONLY: Initial enrollment will include only 3 participants, who may be enrolled into either cohort A or B. Once these three participants have cleared cycle 1, an additional 3 participants may be enrolled into either cohort A or B if no DLTs are seen. If < 2 DLTs are seen in the first 6 participants, enrollment to the rest of the cohorts will proceed. If ≥ 2 DLTs are seen, enrollment will be halted and discussion of dosing change with Merck and the overall PI will occur prior to further enrollment. Based on safety data to date with other platinum-based regimens, we do not anticipate interactions that would necessitate dosing change, so there will not be pre-specified dose reductions planned. Cohorts A and B will be pooled for the purposes of DLT evaluation as the treatment regimen after study initiation is identical.

Cohort C: participants will have previously received 4-6 cycles of platinum-based therapy and have stable disease. In addition, these patients must not be candidates for further consolidation thoracic radiotherapy or PCI. Pembrolizumab treatment should start no sooner than 2 weeks and no later than 6 weeks from the start of the last cycle of chemotherapy. Therapy will continue for up to 34 cycles (2 years).

Cohort D: participants will have previously received 4-6 cycles of platinum-based chemotherapy and thoracic radiation therapy or PCI or both. Pembrolizumab treatment should start no sooner than 2 weeks and no later than 6 weeks from the start of the last dose of radiation. Therapy will continue for up to 34 cycles (2 years).

Treatment will be administered on an outpatient basis. Reported adverse events and potential risks are described in Section 1.8.1. Appropriate dose modifications are described in Section 5. No investigational or commercial agents or therapies other than those described below may be administered with the intent to treat the participant's malignancy.

All patients will be required to have a tissue biopsy within 3 weeks of study entry and after completion of prior therapy (see section 6.6.7.1). For cohort A, this time frame could be up to 6 weeks.

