8.1.6 Survival outcomes

Overall Survival: Overall Survival (OS) is defined as the time from randomization (or registration) to death due to any cause, or censored at date last known alive.

Progression-Free Survival: Progression-Free Survival (PFS) is defined as the time from randomization (or registration) to the earlier of progression or death due to any cause. Participants alive without disease progression are censored at date of last disease evaluation.

Time to Progression: Time to Progression (TTP) is defined as the time from randomization (or registration) to progression, or censored at date of last disease evaluation for those without progression reported.

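### First-line medians of 5.4 (PFS) and 9.5 months (OS) are not valid benchmarks for cohorts B–D or for the pooled population, because 45 of 60 participants enter partway through or after first-line treatment

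*Combined protocol and SAP*

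**What the plan says.** Section 3.3 defines the PFS endpoint as "to evaluate median progression-free survival in overall population with stratification by cohort as compared to historical control of 5.4 months" and the OS endpoint as "to evaluate median overall survival in overall population with stratification by cohort as compared to historical control of 9.5 months". Both values cite reference 31, whose title describes a meta-analysis of carboplatin- or cisplatin-based first-line chemotherapy. In the same section, response rate is restricted to cohort A; PFS and OS are not.

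Section 8.1.6 states that "Progression-Free Survival (PFS) is defined as the time from randomization (or registration) to the earlier of progression or death due to any cause", and OS has the same origin. Nothing is randomized, so time zero is registration, which section 4.5.2 places before protocol therapy.

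Sections 4 and 4.1 set the entry points: A before any chemotherapy, B after one cycle, C after 4-6 cycles, and D after chemotherapy plus thoracic radiotherapy, PCI or both. Section 4.1 bars prior progression in B, C and D; for C the wording is "Participants in cohort C must not have had progression of disease prior to the start of therapy". Section 4.2 adds that "Participants who have had a CR after pre-study therapy are not eligible for study".

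The protocol describes cohort C in three ways. Section 4.1 is as quoted. Section 3.1 says the cohort also takes in "those with chemotherapy-refractory disease (progression within 60 days of completion of treatment with carboplatin-etoposide". Section 5.3 says "participants will have previously received 4-6 cycles of platinum-based therapy and have stable disease".

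Section 9.1 plans Kaplan-Meier estimation, logrank comparisons between study groups and Cox models. It gives no test, alpha or power against 5.4 or 9.5 months.

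**The concern.** A median from the start of first-line treatment is a fair yardstick only for patients whose clock starts there and who are not selected on what happened afterwards. Cohort A can meet that condition. Cohorts B–D cannot: their clocks start weeks to months later, and entry depends on not having progressed and not having reached complete response. Stratifying by cohort separates the curves but gives B–D no comparator of their own.

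The unresolved description of cohort C adds to this. Under section 4.1 its members are selected for being event-free at time zero; under section 3.1 some have already progressed. Neither population matches a first-line control.

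Section 9 lists improved SCLC outcomes with pembrolizumab among the study hypotheses, and 5.4 and 9.5 months are the only external benchmarks that section 3.3 names for PFS and OS. A pooled median on either side of them would invite a conclusion that the design cannot support.

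**Working it through.** The plan states no calculation for this comparison; its only power figure concerns paired PD-L1 differences. The check asks what median from registration each cohort would show if pembrolizumab had no effect.

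**1. Entry times after first chemotherapy** (21-day cycles; 30.44 days per month)
- A: 0.
- B: one cycle, then 3-5 weeks (section 4.1) = 0.7-1.15 months.
- C: day 1 of cycle 4 is week 9 and of cycle 6 is week 15. Adding 2-6 weeks gives weeks 11-21 = 2.5-4.8 months.
- D, earliest: end of cycle 4 (week 12) + 2 weeks = week 14 = 3.2 months, ignoring the length of radiation.
- D, latest: end of cycle 6 (week 18) + 6 weeks, since "Eligible patients for consolidation thoracic radiotherapy will complete this within 6 weeks following completion of chemotherapy" (synopsis, Treatment Plan), + 6 weeks to start = week 30 = 6.9 months. That limit covers thoracic radiotherapy only; PCI alone has none.

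These are pembrolizumab start times; registration falls slightly earlier.

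**2. No-effect median PFS**

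Assume the control clock starts at first chemotherapy, with Weibull survival S(t) = exp[−ln2·(t/5.4)^k]. A cohort entering event-free at time e has median m solving S(e+m)/S(e) = 0.5, so

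m = (e^k + 5.4^k)^(1/k) − e.

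For cohort C with e = 4 and k = 2: √(16 + 29.16) − 4 = 6.72 − 4 = 2.7 months. The pooled median sets the average of the four conditional curves to 0.5. The shape k is not in the documents, so a range is shown. Entry is taken as 0, 0.75, 4 and 5.5 months for A–D.

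| k | A | B | C | D | Pooled |
|---|---|---|---|---|---|
| 0.8 (falling hazard) | 5.4 | 6.1 | 7.2 | 7.5 | 6.5 |
| 1 (constant) | 5.4 | 5.4 | 5.4 | 5.4 | 5.4 |
| 1.5 (rising) | 5.4 | 4.8 | 3.5 | 3.2 | 4.2 |
| 2 (rising) | 5.4 | 4.7 | 2.7 | 2.2 | 3.7 |

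With the latest entry times (0, 1.15, 4.8, 6.9) the pooled range is 3.4-6.7 months. With the earliest (0, 0.7, 2.5, 3.2) it is 4.2-6.3.

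**3. No-effect median OS**

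OS was modelled as PFS plus an exponential post-progression time. Its mean was tuned so that the first-line OS median is 9.5 months (about 3.6, 3.8, 4.3 and 4.75 months at k = 0.8, 1, 1.5 and 2). One million draws were used, conditional on being progression-free at entry.

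- Pooled: 10.6 / 9.5 / 8.3 / 7.9 months.
- Cohort D: about 11.5 / 9.5 / 7.3 / 6.3 months.
- Latest entry, pooled: 10.7 / 9.5 / 8.1 / 7.6 months.

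A simpler model, with Weibull OS conditional only on being alive at mid-window entry, gives pooled 7.6-10.9 months over the same shapes.

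**4. Would counting from first chemotherapy help?**

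No. Time already survived event-free is then guaranteed, and the pooled no-effect PFS median at mid-window entry is 6.4-9.2 months, above 5.4 at every shape.

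**The case against.** The strongest reply is that nothing formal depends on these values. The synopsis labels the objectives secondary/exploratory, the primary endpoint is PD-L1 expression, and no null hypothesis, test or decision rule uses 5.4 or 9.5 months. That is right, and it limits the harm to interpretation. It does not make the comparison valid, and the comparison is written into the endpoint definitions.

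Second, the control's population and time origin are known only from a title, and no Weibull shape is in the documents. At shape 1 the discrepancy disappears, and elsewhere its sign is open. This stands as a limit on the figures, which are illustrations and not replacement benchmarks. The defect itself rests on entry time and eligibility: no single time origin can match all four cohorts.

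Third, the shift is small in places. Cohort B's 4.7-6.1 months lies well inside a 15-patient interval of about 3.4-9.6, and the pooled OS range of 7.6-10.7 lies inside the 60-patient interval of about 7.5-12.4. This is fair: the case is strongest for PFS in C, D and the pool, and weakest for B.

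Fourth, section 3.3 could mean that only the overall estimate is set against the control, with cohorts merely shown separately. The pooled comparison fails on that reading too.

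Fifth, cohort A is an imperfect match as well. Its members may go on to radiotherapy (sections 5.5.5.1 and 5.5.7) and need a life expectancy above 3 months. That stands, and the assumption should be stated.

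**Conclusion.** The concern holds. Cohorts B–D are 45 of 60 participants (75%). They are timed from a later origin than a first-line control and selected on their course to that point, and the plan supplies no matched comparator or adjustment for late entry. With no drug effect, the illustrative pooled median is 3.7-6.5 months for PFS and 7.9-10.6 months for OS; cohort D alone spans 2.2-7.5 and 6.3-11.5 months.

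These figures assume a control clock starting at first chemotherapy, Weibull shapes of 0.8-2 and the entry times shown. They leave out the exclusion of complete responders, selection by radiotherapy candidacy, and any progressors in cohort C. The comparison could flatter or penalise the drug, and the documents do not settle which. Error rates are unaffected; the correction should be made because the pooled, C and D comparisons cannot be interpreted as written.

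**What to change.** - In section 3.3, restrict the comparison with 5.4 and 9.5 months to cohort A, as is already done for response rate. State the assumption that the historical population and time origin match that cohort.
- For B, C and D, report Kaplan-Meier medians and the rates already planned in section 2.2 (PFS at 3 and 6 months, OS at 6 months), from registration, by cohort, with 95% CIs and no historical comparator. Present any pooled median as descriptive only. Align section 9.1.
- Reconcile sections 3.1, 4.1 and 5.3 on whether cohort C includes patients who have progressed. The population at risk at time zero depends on it.

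The cost is wording, plus a historical comparison resting on 15 rather than 60 participants. Assuming exponential times, all d events observed and an estimate equal to the control, the 95% limits are 2d × median / χ² quantiles on 2d degrees of freedom (16.79 and 46.98 for d = 15; 91.57 and 152.21 for d = 60):

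| | 15 participants | 60 participants |
|---|---|---|
| PFS (months) | 3.4-9.6 | 4.3-7.1 |
| OS (months) | 6.1-17.0 | 7.5-12.4 |

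The precision given up belongs to a comparison that does not match its control.
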